8 MATERIALS AND STUDY DRUG

Not applicable.

This study is designed to capture pharmacokinetics information on bismuth and TMB in a naturalistic real-world setting. No study medication *per se* will be distributed during the course of this study. The patient will be instructed to take the Pylera® as prescribed by the Investigator.

9 STUDY PROCEDURES

The study procedures pertaining to the conduct of the study and as well as a detailed description of study procedures to be performed are summarized in Appendix 1 (Study Flowchart).

9.1 INCLUSION PROCEDURES

9.1.1 Informed Consent / Instructions to subjects

Before a subject is enrolled in this study and prior to the performance of any evaluations or study procedures, the Investigator or designee must explain the study to the subject in sufficient detail to allow for her/his informed decision to participate. The Investigator must adopt a standardized approach for obtaining Informed Consent from each subject. Availability of alternative treatment must be fully explained to the subject and documented in the Informed Consent Form (ICF). If the subject understands the requirements of the study and agrees to participate, the subject will sign the ICF. This form must also be signed by the Investigator or designee. All signatures must be dated. If the Investigator chooses to alter a medical regimen of the subject for the purpose of enrolling the subject in this study, the Informed Consent for the study should be signed at that time and prior to any alteration in the subject's ongoing therapeutic regimen. A copy of the signed and dated consent form must be given to the subject before the subject initiates the study. The signed ICF must be available for an Aptalis Pharma US, Inc. CRA or designee for on-site review. Upon willingness to participate in the study, each subject will be enrolled in the study by assignment of a unique sequential enrollment number for each study site.

9.1.2 Observations and Measurements

Following the granting of Informed Consent, each subject will be assigned a subject number in sequential order.

The following Inclusion Visit procedures and evaluations in addition to procedures normally conducted as part of standard of care will be performed after Informed Consent will be recorded in the appropriate sections of the CRF:

- Demographic data
- Confirmation of inclusion and exclusion criteria
- Date of Pylera® prescription
- Name of prescribed PPI
- Vital signs measurement (blood pressure, pulse rate), height and weight
- Disease history regarding *H. pylori* infection with previous *H. pylori* treatment and diagnostic tests with date and results (negative/positive)
- Co-morbidities, medical/surgical history
- Recording of prior and concomitant medications

Subjects will provide one blood sample as the baseline sample (D0 sample) for assessment of plasma and whole blood bismuth concentrations and whole blood trimethylbismuth (TMB) concentrations as per the procedures outlined in Appendix 2.

Once the D0 sampling is complete, subjects will be given an appointment for the second blood sampling (D11 sample) and subjects may initiate treatment with Pylera®.

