3.2 SCHEDULING OF VISITS

Patient inclusion in the study will be considered after the decision to treat with Pylera® has been made by the Investigator.

The Inclusion Visit will be initiated following signature of Informed Consent.

Information regarding date of Pylera® prescription, name of prescribed PPI, demographic data, vital signs, height, weight, disease history for *H. pylori* infection (including information pertaining to prior *H. pylori* treatment), co-morbidities, medical and surgical history — will be surveyed, as well as information concerning diagnostic procedures performed to verify *H. pylori* infection.

Upon confirmation of eligibility, subjects will be given instructions for the first blood sample (D0 sample) for bismuth and TMB PK prior to initiating treatment with Pylera®, and an appointment for the second blood sampling.

Upon completion of the 10-day treatment with Pylera®, subjects will proceed to the EOT Visit to provide the second blood sample (D11 sample) for bismuth and TMB PK.

Subjects who demonstrate clinical symptoms indicative of bismuth-related neurological adverse events or bismuth accumulation at the EOT Visit (total bismuth in whole blood > 50 µg/L) will be requested to return to the laboratory immediately to draw a third blood sample for evaluation of bismuth. Subjects having clinical symptoms indicative of bismuth-related neurological adverse events will be referred to the separate Intensive Monitoring Program. If bismuth concentration remains sustained in subjects with no neurological symptoms and subject interview with Investigator confirms that no third-party source of bismuth was consumed outside of the context of this study, the subject will be referred to the separate Intensive Monitoring Program to be evaluated for inclusion.

A diagnostic *H. pylori* test (breath test, biopsy, or other test at the discretion of the Investigator) to assess *H. pylori* eradication should be repeated on one single occasion at least 28 days post-treatment as part of the EOS Visit.

Vital signs, concomitant medications, adverse events (AEs) and the presence of central nervous system (CNS) adverse events of interest as listed in Appendix 3 will be assessed at the EOT and EOS Visits.

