9.4 OTHER PROCEDURES

A diagnostic *H. pylori* test (breath test, biopsy, or other test at the discretion of the Investigator)

[figure not shown]
Presence of *H. pylori* will be assessed at the EOS Visit. The selection of the method for this assessment is at the discretion of the Investigator.

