11.5.1 Data Capture

Simplified data collection to characterize subject profile will be conducted using a paper-based multi-part CRF, which will capture:

- socio-demographic data, including age, sex, height, weight
- screening/baseline parameters prior to prescription of Pylera®, including medical history, vital signs, and results of a diagnostic *H. pylori* test (breath test, biopsy, or other test at the discretion of the Investigator) (if available), prescribed treatments, including:
 - Pylera® (indication, dose and duration of treatment)
 - PPI (indication, dose and duration of treatment)
 - other concomitant treatment(s)
- prior and concomitant medications
- AEs
- CNS AEs

A specific form will be completed by the subject and/or sampling laboratory to capture data related to PK blood draw. This form will capture subject characteristics, time of drug ingestion, time of sample, time elapsed since first drug intake, and time elapsed since last drug intake. This specific form will be completed at each blood draw and will be sent with each sample.

A specific form entitled “Targeted follow-up form – Pylera® eradication therapy failure” will be used to document subjects who demonstrate a positive diagnostic *H. pylori* test (breath test, biopsy, or other test at the discretion of the Investigator) infection at the EOS Visit. This form will permit a systematic assessment of the post-marketing case reports of lack of efficacy.

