16 APPENDICES

APPENDIX 1 – STUDY FLOWCHART

APPENDIX 2 – PHARMACOKINETICS BLOOD SAMPLING

APPENDIX 3 – CENTRAL NERVOUS SYSTEM ADVERSE EVENTS OF INTEREST

APPENDIX 1 - STUDY FLOWCHART

	Inclusion Visit (Day 0)	End of Visit (Day 11)	End of Study Visit (Day 39)
Informed Consent	X		
Demographics	X		
Inclusion/Exclusion criteria	X		
Vital Signs	X	X	X
Diagnostic tests done before Pylera® prescription ¹	X		
Co-morbidities, medical, surgical history	X		
Concomitant medications	X	X	X
Diagnostic H. pylori test (breath test, biopsy, or other test)	X		X ²
Pharmacokinetics sample	X	X ³	
Adverse events		X	X
CNS adverse events ⁴		X	X

1. Including information pertaining to prior *H. pylori* treatment.
2. At the discretion of the Investigator
3. Subjects who demonstrate bismuth accumulation at the End of Treatment Visit (> 50 µg/L) will be referred to the separate Intensive Monitoring Program to be evaluated for inclusion. In case of inclusion, patients will be requested to return to the laboratory to draw a third blood sample for evaluation of bismuth). In case of neurological AE indicative of bismuth encephalopathy (please refer to Appendix 3 – Central Nervous System Adverse Events of Interest) if present at Day 11 blood samples will be as quickly processed as possible.
4. For CNS adverse event indicative of encephalopathy, follow-up will be perform by Intensive Monitoring Program

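### The flowchart marks a baseline H. pylori test that the procedures sections do not contain, and the eradication analysis omits the initially positive restriction of secondary objective 1

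*Protocol*

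**What the plan says.** **Appendix 1 (flowchart).** Two rows concern H. pylori testing, and both carry a mark at Day 0.
- "Diagnostic tests done before Pylera® prescription" is marked at the Inclusion Visit only. Its footnote adds information on prior treatment.
- "Diagnostic H. pylori test (breath test, biopsy, or other test" is marked at the Inclusion Visit and at the EOS Visit. The footnote "At the discretion of the Investigator" is attached to the EOS mark alone, so the Day 0 mark is unqualified.

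**Text sections.**
- Section 3.2 has the Inclusion Visit survey "information concerning diagnostic procedures performed to verify *H. pylori* infection", that is, procedures already done.
- Section 9.1.2 lists the Inclusion Visit procedures. The only relevant item is disease history with "previous *H. pylori* treatment and diagnostic tests with date and results (negative/positive".
- Section 9.4, on the study's own test, says that presence of the organism "will be assessed at the EOS Visit. The selection of the method for this assessment is at the discretion of the Investigator".
- Section 11.5.1 captures "screening/baseline parameters prior to prescription of Pylera®, including medical history, vital signs, and results of a diagnostic" test, described as "breath test, biopsy, or other test at the discretion of the Investigator) (if available".

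**Objective and analysis.** Secondary objective 1 (synopsis and section 2.2) evaluates eradication in subjects whose initial test was positive. Section 11.7.4.2 defines the eradication rate as the proportion of negative tests at least 28 days after treatment and calculates it in the Safety and Per Protocol Populations. It sets no condition on baseline status.

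**The concern.** Section 3.1 points to section 9 and Appendix 1 together as the detailed description of procedures and gives neither precedence. A site working from the flowchart could perform a breath test or biopsy at Day 0 in every subject. A site working from section 9.1.2 would transcribe whatever results already exist. Baseline infection status could then be complete at some sites and partial at others, and some subjects would have a procedure that section 9 does not list.

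Baseline status matters because entry does not guarantee infection. Section 4.2.1 requires a prescription, not a positive test. The synopsis calls subjects presumed positive. Section 11.7.3 allows for prescribing decisions reached by clinical evaluation. Objective 1 deals with this by restricting itself to initially positive subjects, but section 11.7.4.2 does not carry the restriction over. An eradication rate that includes people who never had a documented infection does not answer objective 1, and the error runs towards a higher rate.

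**Working it through.** The protocol gives no figure to reproduce here: section 11.1 states that no sample-size or power calculation was made. The finding rests on comparing the sections. The arithmetic only shows scale.

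**1. Is a Day 0 test scheduled?**

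| Place | Inclusion Visit | EOS Visit |
|---|---|---|
| Appendix 1, row for earlier tests | marked | not marked |
| Appendix 1, row for the diagnostic test | marked, no footnote | marked, discretion footnote |
| 3.2 | existing results surveyed | test repeated once |
| 9.1.2 | existing results recorded as history | not covered |
| 9.4 | none | test assessed |
| 11.5.1 | result captured where one exists | positive results documented on a form |

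Only the second flowchart row implies a test performed at Day 0. The row above it already covers recording of earlier tests, and at EOS the same mark in the second row means a test that is carried out.

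**2. Does the analysis set match the objective?** The Safety Population (11.7.1.3) is all enrolled subjects who consented. The Per Protocol Population (11.7.1.2) requires both blood samples and no major violation. Neither uses a baseline H. pylori result. A subject in either set with no baseline result and a negative EOS test is therefore counted as eradicated.

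**3. Size of the upward shift (illustration).** Let p be the true eradication rate in infected subjects and q the share of analysed subjects who were uninfected at entry and test negative at EOS. Then

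observed rate = (1 - q)p + q, so the shift is q(1 - p).

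The values of p come from section 1.1 (93.3% and 87.7% in earlier Phase III trials). The values of q are assumptions.

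| p | q = 10% | q = 20% | q = 30% |
|---|---|---|---|
| 93.3% | 94.0% | 94.6% | 95.3% |
| 87.7% | 88.9% | 90.2% | 91.4% |

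The shift is 0.7 to 2.0 points at 93.3% and 1.2 to 3.7 points at 87.7%. If every recorded positive is a true positive, q cannot exceed the share without a documented positive test. Setting q equal to that share is therefore the extreme case.

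**4. Precision cost of restricting the denominator.** The 95% half-width is 1.96 × sqrt(0.9 × 0.1 / n), taking 90% eradication and assuming that 10-30% of the planned 200 have no test.

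| n | half-width (points) |
|---|---|
| 200 | 4.16 |
| 180 | 4.38 |
| 160 | 4.65 |
| 140 | 4.97 |

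Exact (Clopper-Pearson) intervals near 93.3% give a similar picture: 187/200 gives 89.1% to 96.5% (width 7.4 points), and 149/160 gives 88.0% to 96.5% (width 8.5 points).

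**The case against.** The best reply is that the flowchart is only a summary. Section 9 itself describes Appendix 1 in that way. Section 9.1.2 says its procedures come on top of standard care, and inclusion follows the decision to treat (section 3.2). The Day 0 mark could thus stand for recording the test that led to the prescription. Footnote 1 ties the other row to prior treatment, so the two rows could be meant to match the two halves of the item in section 9.1.2.

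This has force. A reader might infer that the two schedules cannot both be followed, but the documents do not go that far: section 9.1.2 does not forbid a test. What remains is ambiguity. The reading by footnote is not what the row labels say, the mark carries no discretion footnote at Day 0, and section 3.1 gives Appendix 1 equal standing with section 9.

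A second reply is that the SAP, which section 11.7 promises before database lock, can define the subset. It can choose among several baseline results. But section 11.7.4.2 already names analysis sets that do not match the objective, so this conflict lies within the protocol.

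Two stronger inferences also fail.
- A reader might conclude that the success and failure groups of objectives 2 and 4 would also change with site practice. As written in section 2.2, those objectives carry no initially positive restriction, and section 11.7.6 splits the Safety Population by outcome with no baseline condition.
- A reader might try to count subjects whose Day 0 test contradicts an earlier positive. The protocol gives neither the frequency of Day 0 testing nor the sensitivity of the tests, so any such count would rest wholly on assumption.

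**Conclusion.** The point holds as two linked inconsistencies. First, Appendix 1 marks a baseline test that sections 3.2, 9.1.2, 9.4 and 11.5.1 do not provide for, so sites may differ on whether it is done. Second, section 11.7.4.2 does not apply the restriction that defines objective 1, so subjects without documented infection can count as eradicated.

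The rate as defined in 11.7.4.2 does not itself vary with Day 0 testing, because neither of its populations uses a baseline result. Site practice affects only who can be identified as initially positive for objective 1.

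The size is modest: under the assumed 10-30% uninfected, the upward shift is about 1 to 4 points. The protocol supplies no figure for that share. The endpoint is secondary and descriptive, and the primary bismuth objective is unaffected. The correction is worth making because it is cheap and because the rate as defined does not answer the stated objective.

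**What to change.** 1. Make Appendix 1 and section 9.1.2 agree. The cheapest way is to remove the Day 0 mark from the diagnostic test row, since the row above already covers earlier tests. If the sponsor did intend a Day 0 test, section 9.1.2 should list it, and sections 9.4 and 11.5.1 should be brought into line.
2. In section 11.7.4.2, base the objective 1 eradication rate on subjects with a positive pre-treatment test, recorded under section 9.1.2 as the basis for the current prescription. Report subjects without such a result separately.

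A rule that takes the most recent result before the first dose would be a poor substitute. If a Day 0 test were kept, a negative result then would override the positive test on which treatment was prescribed.

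The cost is one flowchart mark and one or two sentences, with no new data if the mark is removed. The downsides are the smaller denominator (half-width 4.4-5.0 instead of 4.2 points under the assumptions above) and that infection status stays unknown for subjects prescribed without a test.

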9.1.3 Randomization Procedures

There is no randomization procedure as this is an open-label, single-arm study.

9.2 DURING TREATMENT PROCEDURES

- Recording of AEs in case a patient contact the Investigator

9.2.1 Subjects who completed treatment with Pylera®

Subjects who have completed the 10-day treatment with Pylera® will return to complete the following procedures as part of the EOT Visit:

- Vital signs measurement (blood pressure, pulse rate)
- Recording Pylera® treatment description and compliance
- Recording of concomitant medications
- Recording of AEs

The presence of CNS adverse events of specific interest as listed in Appendix 3 will be assessed at this visit with the specific form “Pharmacovigilance reporting form-neurological disorders and bismuth” developed for the collection of the adverse events of special interest as part of the Intensive Monitoring Program that will be completed by the Investigator.

Subjects will provide one blood sample as the post-treatment sample (D11 sample) for assessment of plasma and whole blood bismuth concentrations as well as whole blood TMB concentrations as per the procedures outlined in Appendix 2.

Subjects who demonstrate bismuth accumulation in whole blood at the EOT Visit ($> 50 \mu\text{g/L}$) will be requested to return immediately to the laboratory to draw a third blood sample for evaluation of bismuth. If bismuth concentration remains sustained and subject interview with Investigator confirms that no third-party source of bismuth was consumed outside of the context

of this study, the subject will be referred to the separate Intensive Monitoring Program to be evaluated for inclusion.

Subjects will return 28 days after the EOT Visit to complete the EOS Visit. At this visit, subjects will complete:

- Vital signs measurement (blood pressure, pulse rate)
- Recording eradication test
- Recording of concomitant medications
- Recording of AEs

The presence of CNS adverse events of specific interest as listed in Appendix 3 will be assessed at this visit with the specific form “Pharmacovigilance reporting form-neurological disorders and bismuth” developed for the collection of the adverse events of special interest as part of the Intensive Monitoring Program that will be completed by the Investigator.

Subjects who demonstrate a positive diagnostic *H. pylori* test (breath test, biopsy, or other test at the discretion of the Investigator) at End of Study will be documented by the completion of a specific form entitled “Targeted follow-up form – Pylera® eradication therapy failure”. These subjects will be referred to treatment for *H. pylori* infection outside of the context of this study.

9.2.2 Subjects who prematurely discontinue treatment with Pylera®

For any subject who prematurely discontinues treatment with Pylera®, the Investigator will perform the EOS procedures and will complete appropriate pages of the CRF. A diagnostic *H. pylori* test (breath test, biopsy, or other test) will be conducted at the discretion of the Investigator.

In case of withdrawal of consent, only the date of and the reason for withdrawing consent will be collected on the CRF. Otherwise, the Investigator will make all reasonable effort to complete as much as possible the following at the time of discontinuation.

#	Information to be collected
1	Vital sign measurements (pulse rate, blood pressure measured from the same arm throughout the study)
2	Record of any occurrence of AEs, change in concurrent medical conditions, use of adjunctive therapy/procedure, and intake of concomitant medication
3	Collect safety information via a phone call to the patient 30 ± 5 days after discontinuation (includes AEs, change in concurrent medical conditions, use of adjunctive therapy/procedures, and intake of concomitant medication).

4	A diagnostic H. pylori test (breath test, biopsy, or other test) at the discretion of the Investigator
---	--

All results of evaluation and observations, together with the reason for withdrawal from the study, will be recorded on the CRF.

For any subject who prematurely discontinues treatment with Pylera® due to a neurological AE indicative of bismuth encephalopathy, the subject will be followed up through a separate Pylera® Intensive Monitoring Program.

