For any subject who leaves the study, the Investigator must complete the CRF up to the time of withdrawal, ascertain the reason for discontinuation, and perform the EOS procedures. All reasonable efforts must be made to contact subjects who fail to return for scheduled visits and to encourage them to comply with the procedure. All attempts to contact subjects either by phone, courier, and/or email must be clearly documented. In case of withdrawal of consent, the date of withdrawal and the reason for withdrawing consent if provided by the subject will be collected. No additional data will be collected from the time of withdrawal of consent.

In the case of premature voluntary withdrawal of a subject with the premature stop of treatment with Pylera®, the subject will be excluded from the study and will be monitored separately. For subjects who have halted treatment with Pylera® and have withdrawn due to a neurological AE indicative of bismuth encephalopathy, the subject will be followed up through a separate Pylera® Intensive Monitoring Program.

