10 ADVERSE EVENTS

Subjects receiving any investigational drug require careful observation. Any adverse event/concurrent illness experienced by a subject during any portion of the study must be described in detail and be fully evaluated by the Investigator. The Investigator is responsible for recording all adverse events observed or reported during the study from Inform Consent signature until date of completion/discontinuation, regardless of the drug-related assessment and/or clinical significance. Any pertinent information must be recorded in the CRF and additional comments describing the course and outcome of these events should be provided as appropriate.

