11.7.1.3 Safety Population

The Safety Population will be defined as all enrolled subjects who have provided informed consent.

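### Section 9.2.2 limits the CRF to date and reason on withdrawal of consent, in conflict with sections 4.6 and 10, so adverse events known but not yet entered may go unrecorded

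*Protocol*

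**What the plan says.** Protocol section 9.2.2, on subjects who stop Pylera early, gives this rule: "In case of withdrawal of consent, only the date of and the reason for withdrawing consent will be collected on the CRF". It continues: "Otherwise, the Investigator will make all reasonable effort to complete as much as possible the following at the time of discontinuation". The list that follows covers vital signs, any AEs and changes in medication, a later safety telephone call and an *H. pylori* test.

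Section 4.6 sets a different rule. In general, "For any subject who leaves the study, the Investigator must complete the CRF up to the time of withdrawal". On withdrawal of consent the date is recorded, with the reason if the subject gives one, and then: "No additional data will be collected from the time of withdrawal of consent". The cut-off is a point in time, not a restriction to two items.

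Section 10 adds: "The Investigator is responsible for recording all adverse events observed or reported during the study from Inform Consent signature until date of completion/discontinuation". Section 10.4.3.2 puts all AEs on the CRF's AE form, and section 7 requires first-dose and last-dose details in the CRF.

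During treatment, section 9.2 provides only for this: "Recording of AEs in case a patient contact the Investigator". The flowchart in Appendix 1 first marks AEs at Day 11.

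For the analysis, section 11.7.1.3 states: "The Safety Population will be defined as all enrolled subjects who have provided informed consent". Section 11.7.1.4 specifies observed cases without imputation, and section 11.7.6 reports the number and percentage of subjects with any AE.

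**The concern.** A site following 9.2.2 and a site following 4.6 would complete different CRFs for the same subject. The difference concerns the period before withdrawal. Both sections agree that nothing is gathered for the period after it.

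The design makes that earlier period vulnerable. A subject who withdraws consent on, say, Day 5 has had no scheduled AE assessment since inclusion. The contact at which the subject announces withdrawal may be the first and last occasion to enter events that have already happened. Appendix 3 events are assessed only at the Day 11 and Day 39 visits, so the same applies to them. An AE is a plausible reason to leave, so these subjects may have more AEs than the rest.

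At stake is the completeness of the AE tables. An analysis plan cannot recover data that were never entered.

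**Working it through.** **1. The sections side by side**

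| Section | Subject withdraws consent: period before withdrawal | Period after |
|---|---|---|
| 9.2.2 | Date and reason only; AE record reserved for other discontinuations | Nothing |
| 4.6 | CRF completed up to withdrawal | Nothing further |
| 10 and 10.4.3.2 | All AEs from consent to discontinuation, on the CRF | Not addressed for withdrawal of consent |

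The conflict lies in the middle column. The AE item in the 9.2.2 list asks for any occurrence of AEs, so it looks back over time already elapsed. Withholding it from subjects who withdraw consent removes a retrospective record, not only follow-up.

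**2. Size, under stated assumptions**

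The protocol gives no withdrawal rate, no expected AE rate for these subjects and no power calculation, so there is no figure of its own to reproduce. Inputs:
- N = 200 (section 4.1).
- w = number withdrawing consent during treatment: 4, 10 or 20 (assumed; 2%, 5% or 10%).
- p = share of them with an AE not yet on the CRF: 0.6 to 0.9 (assumed).
- Withdrawn subjects stay in the denominator, and the site applies 9.2.2 literally.

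Understatement of the percentage with any AE = 100 × w × p / 200:
- w = 4: 100 × 4 × 0.6 / 200 = 1.2, up to 100 × 4 × 0.9 / 200 = 1.8 points.
- w = 10: 3.0 to 4.5 points.
- w = 20: 6.0 to 9.0 points.

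**3. A milder scenario**

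Take the one AE rate that the protocol reports, headache in 7/32 = 21.9% of subjects in the earlier PK study (section 1.1). Suppose that withdrawn subjects have the same rate as everyone else and that all their events are lost. Then reported % = 21.88 × (1 − w/200):
- w = 2: 21.66, a loss of 0.2 points.
- w = 4: 21.44, a loss of 0.4.
- w = 10: 20.78, a loss of 1.1.
- w = 20: 19.69, a loss of 2.2.

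This covers one type of AE and assumes no link between AEs and withdrawal. It therefore sits at the low end for the percentage with any AE.

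**4. If withdrawn subjects leave the denominator**

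Section 4.6 says that a subject who voluntarily withdraws and stops Pylera early is excluded from the study, which sits badly with section 11.7.1.3. For an event type with no cases, the exact one-sided 95% upper bound is 1 − 0.05^(1/n): 1.49% at n = 200, 1.52% at n = 196 and 1.65% at n = 180. The denominator choice alone changes little. The unrecorded events matter more.

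**The case against.** The best defence is contextual. The restrictive sentence is followed at once by one that opens with Otherwise and refers to work done at the time of discontinuation. It can be read as replacing that work-up only, which would agree with 4.6. Other sections still bind the site. AEs are to be recorded promptly (10.4.1), serious AEs go on the CRF form within 24 hours of awareness (10.4.3.1), and AEs are recorded whenever a patient makes contact during treatment (9.2), which announcing withdrawal normally is. The group is also narrow, because stopping Pylera without withdrawing consent brings the full list.

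Much of this stands, and it rules out stronger readings. A reader might infer that AEs before withdrawal never reach the CRF. The documents do not support that: 9.2.2 deletes nothing already entered, and the duties above remain. A reader might also infer that these subjects are counted as event-free. The protocol does not say so. That would be the effect of a plain n/N table, and 4.6 leaves their place in the denominator unclear. Nor is a neurological case simply lost, since sections 4.6, 9.2.2 and 10.4.3.3 send such cases to the separate Intensive Monitoring Program, although that lies outside this study's tables.

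The defence does not remove the conflict. The benign reading depends on overlooking the word only and the retrospective AE item that these subjects do not get.

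**Conclusion.** The inconsistency is real and should be corrected. Section 9.2.2 read literally narrows what 4.6 and section 10 require for the period before withdrawal of consent. AEs known to the investigator but not yet entered may be left off the CRF, and AE percentages could then be understated.

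The effect is probably small: about 1 to 2 points at 2% withdrawal if most withdrawn subjects had an unrecorded AE, and less if their AE risk is ordinary. The larger values in the working need 5% to 10% withdrawal of consent and should not be read as expected. Every figure rests on assumed withdrawal and AE rates, on literal use of 9.2.2 and on keeping these subjects in the denominator. The AE summaries are descriptive, and the conclusion on bismuth toxicity in section 11.7.7 rests on concentrations, so that conclusion is not directly affected.

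**What to change.** Replace the sentence in 9.2.2 with wording that follows 4.6 and section 10, for example:

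*On withdrawal of consent, the date and, if given, the reason are recorded. Data known to the investigator for the period up to that date (AEs including Appendix 3 events, first and last dose, concomitant medications) are entered in the CRF and kept. No data are collected for the period after that date.*

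In the same amendment, reconcile the statement in 4.6 that voluntary withdrawers who stop treatment are excluded from the study with the Safety Population in 11.7.1.3, so that it is clear whether they count in the safety denominator.

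The cost is a short text amendment. It adds no visit, sample or procedure, and it respects withdrawal of consent because 4.6 already sets the same cut-off.
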